12.2 Efficacy Secondary Endpoints

Endpoint: Components of the primary endpoint: proportion of eyes with CRR of VA from BL at Month 12 compared to matching external NH control group

Analysis method: This endpoint will be analysed with methods similar as for analysing the primary endpoint as defined in section The criteria of inclusion/exclusion for the pre-planned indirect comparison of the primary endpoint against an external natural history control group, where it is only considered who are carriers of only one of the three major LHON mtDNA (G11778A, G3460A or T14484C). Due this criterion, efficacy analysis where there is an indirect comparison to the external natural history control group, will be based on the mITT population.

Primary endpoint 12.1.

Endpoint: Components of the primary endpoint: proportion of eyes in which BL VA better than 1.0 logMAR was maintained at Month 12 compared to matching external NH control group

Analysis method: This endpoint will be analysed with methods similar as for analysing the primary endpoint as defined in section The criteria of inclusion/exclusion for the pre-planned indirect comparison of the primary endpoint against an external natural history control group, where it is only considered who are carriers of only one of the three major LHON mtDNA (G11778A, G3460A or T14484C). Due this criterion, efficacy analysis where there is an indirect comparison to the external natural history control group, will be based on the mITT population.

Primary endpoint 12.1.

Endpoint: Proportion of eyes in patients treated with Raxone[®]>1 year after the onset of symptoms with CRR of VA from BL or in which BL VA better than 1.0 logMAR was maintained at Month 12 compared to external NH control group

Analysis method: This endpoint will be analysed with methods similar as for analysing the primary endpoint as defined in section The criteria of inclusion/exclusion for the pre-planned indirect comparison of the primary endpoint against an external natural history control group, where it is only considered who are carriers of only one of the three major LHON mtDNA (G11778A, G3460A or T14484C).

Study: SNT-IV-005

Due this criterion, efficacy analysis where there is an indirect comparison to the external natural history control group, will be based on the mITT population.

Primary endpoint 12.1.

Endpoint: Proportion of eyes and patients treated with Raxone® ≤1 year after the onset of symptoms with CRR of VA from BL or in which BL VA better than 1.0 logMAR was maintained following 6, 18 and 24 months of treatment with Raxone® compared to matching external NH control group

Analysis method: This endpoint will be analysed separately for each follow-up with methods similar as for analysing the primary endpoint as defined in section The criteria of inclusion/exclusion for the pre-planned indirect comparison of the primary endpoint against an external natural history control group, where it is only considered who are carriers of only one of the three major LHON mtDNA (G11778A, G3460A or T14484C). Due this criterion, efficacy analysis where there is an indirect comparison to the external natural history control group, will be based on the mITT population.

Primary endpoint 12.1.

Endpoint: Proportion of eyes/patients treated with Raxone® ≤1 year after the onset of symptoms with "Off-chart" VA at BL in whom VA improves to better than 1.60 logMAR by Month 6, 12, 18 and 24

Analysis method: This endpoint will be analysed by means of descriptive statistics in the LEROS ITT population and presented in contingency tables with frequencies and percentages as illustrated in section 19.2.

Endpoint: Proportion of eyes/patients treated with Raxone® >1 year after the onset of symptoms with "Off-chart" VA at BL in whom VA improves to better than 1.60 logMAR by Month 6, 12, 18 and 24

Analysis method: This endpoint will be analysed by means of descriptive statistics in the LEROS ITT population and presented in contingency tables with frequencies and percentages as illustrated in section 19.2.

Endpoint: Proportion of eyes/patients treated with Raxone® \leq 1 year after the onset of symptoms with VA in the categories of better than 1.0 logMAR, 1.0 to 1.68 logMAR and above 1.68 logMAR at each assessment time point up to Month 24

Analysis method: This endpoint will by means of descriptive statistics in the LEROS ITT population and presented in contingency tables with frequencies and percentages as illustrated in section 19.2.

Endpoint: Proportion of eyes/patients treated with Raxone® >1 year after the onset of symptoms with VA in the categories of better than 1.0 logMAR, 1.0 to 1.68 logMAR and above 1.68 logMAR at each assessment time point up to Month 24

Analysis method: This endpoint will by means of descriptive statistics in the LEROS ITT population and presented in contingency tables with frequencies and percentages as illustrated in section 19.2.

12.3 Additional efficacy analysis

Outcome: Proportion of eyes and patients treated with Raxone® ≤1 year after the onset of symptoms with Clinically Relevant Worsening (CRW) of VA from BL at Month 12 compared to matching external NH control group.

Analysis method: This outcome will by means of descriptive statistics

Outcome: Proportion of eyes and patients treated with Raxone® >1 year after the onset of symptoms with Clinically Relevant Worsening (CRW) of VA from BL at Month 12 compared to matching external NH control group.

Analysis method: This outcome will by means of descriptive statistics

Outcome: Proportion of eyes and patients treated with Raxone® ≤1 year after the onset of symptoms with Clinically Relevant Worsening (CRW) of VA from BL at Month 24 compared to matching external NH control group.

Analysis method: This outcome will by means of descriptive statistics

Outcome: Proportion of eyes and patients treated with Raxone® >1 year after the onset of symptoms with Clinically Relevant Worsening (CRW) of VA from BL at Month 24 compared to matching external NH control group.

Analysis method: This outcome will by means of descriptive statistics

Outcome: Eyes with CRR (and related information, Table 12-1) from BL at 24 months considering time symptoms onset in the most recent affected eye at BL.

Analysis method: This outcome will be analysed by means of descriptive statistics and a complementary analysis using Kaplan-Meier method in the LEROS ITT population and in the subgroups specified in section 9.3. Survival analysis will use CRR as an event, months in treatment at CRR as time of event, and months at last assessment during treatment as censoring. It will be presented the cumulative percent curve of CRR using months since BL at CRR as variable. Inverse Kaplan-Meier curves of time (in months) to CRR (with number of eyes at risk and censored at 6, 12, 18 and 24 months) will be presented.

Table 12-1 - LEROS ITT eyes with CRR from BL at 24 months

	Variable	Analysis sets				
Eyes with CRR from BL	Type ¹	LEROS ITT	mtDNA subgroups ⁴	Age at BL subgroups 4	Best VA BC at BL subgroups 4	
CRR	N	Х	Х	Х	х	
Months in treatment since BL at CRR ²	С	Х	Х	Х	Х	
Time in treatment at CRR by follow-up ^{2,3}	N	Х	Х	Х	Х	
Change in logMAR compared to BL at CRR ²	С	Х	х	Х	Х	
Change in logMAR compared to BL at 24 months ²	С	х	х	Х	х	
CRR Kaplan-Meier analysis	-	Х	х	Х	х	

¹ Variable Type: nominal (N), ordinal (O), continuous (C); ² Only eyes with CRR from BL should be accounted; ³ Time in treatment categories defined in section 16; ⁴ Subgroups are to be analysed as defined in 9.3;

Outcome: Patients with CRR from BL at 24 months (and related information, Table 12-2) considering time symptoms onset in the most recent affected eye at BL.

Analysis method: This outcome will be analysed by means of descriptive statistics and a complementary analysis using Kaplan-Meier method in the LEROS ITT population and in the subgroups specified in section 9.3. Survival analysis will use CRR as an event, months in treatment at CRR as time of event, and months at last assessment during treatment as censoring. It will be presented the cumulative percent curve of CRR using months since BL at CRR as variable. Inverse Kaplan-Meier curves of time (in months) to CRR (with number of patients at risk and censored at 6, 12, 18 and 24 months) will be presented.

SNT-IV-005 Statistical Analysis Plan

Confidential

Table 12-2 – LEROS ITT patients with CRR from BL at 24 months

		Analysis sets				
Patients with CRR from BL	Variable Type ¹	LEROS ITT	mtDNA subgroups ⁴	Age at BL subgroups 4	Best VA BC at BL subgroups 4	
CRR	N	Х	Х	Х	Х	
Months in treatment since BL at CRR ²	С	Х	Х	X	Х	
Time in treatment at CRR by follow-up ^{2,3}	N	Х	X	X	Х	
Change in logMAR compared to BL at 1st CRR ²	С	Х	X	X	Х	
Best change in logMAR compared to BL at 24 months ²	С	х	Х	Х	х	
CRR Kaplan-Meier analysis	-	х	х	Х	Х	

¹ Variable Type: nominal (N), ordinal (O), continuous (C); ² Only eyes with CRR from BL should be accounted; ³ Time in treatment categories defined in section 16; ⁴ Subgroups are to be analysed as defined in 9.3;

Outcome: Eyes with CRR (and related information, Table 12-1) from Nadir (as defined in section 16) at 24 months considering time symptoms onset in the most recent affected eye at BL.

Analysis method: This outcome will be analysed by means of descriptive statistics and a complementary analysis using Kaplan-Meier method in the LEROS ITT population and in the subgroups specified in section 9.3. Survival analysis will use CRR as an event, months in treatment at CRR as time of event, and months at last assessment during treatment as censoring. It will be presented the cumulative percent curve of CRR using months since BL at CRR as variable. Inverse Kaplan-Meier curves of time (in months) to CRR (with number of eyes at risk and censored at 6, 12, 18 and 24 months) will be presented.

Table 12-3 - LEROS ITT eyes with CRR from Nadir at 24 months

	Variable		Analysis sets				
Eyes with CRR from Nadir	Variable Type ¹	LEROS ITT	mtDNA subgroups ⁴	Age at BL subgroups 4	Best VA BC at BL subgroups 4		
CRR	N	х	х	Х	х		

SNT-IV-005 Statistical Analysis Plan

Confidential

Months in treatment since BL at CRR ²	С	Х	Х	Х	х
Time in treatment at CRR by follow-up ^{2,3}	N	Х	Х	Х	х
Change in logMAR compared to BL at CRR ²	С	Х	Х	Х	х
Change in logMAR compared to BL at 24 months ²	С	Х	х	Х	х
CRR Kaplan-Meier analysis	-	Х	х	х	Х

Variable Type: nominal (N), ordinal (O), continuous (C); Only eyes with CRR from Nadir should be accounted; Time in treatment categories defined in section 16; Subgroups are to be analysed as defined in 9.3;

Outcome: Patients with CRR from Nadir (as defined in section 16) at 24 months (and related information, Table 12-2) considering time symptoms onset in the most recent affected eye at BL.

Analysis method: This outcome will be analysed by means of descriptive statistics and a complementary analysis using Kaplan-Meier method in the LEROS ITT population and in the subgroups specified in section 9.3. Survival analysis will use CRR as an event, months in treatment at CRR as time of event, and months at last assessment during treatment as censoring. It will be presented the cumulative percent curve of CRR using months since BL at CRR as variable. Inverse Kaplan-Meier curves of time (in months) to CRR (with number of patients at risk and censored at 6, 12, 18 and 24 months) will be presented.

Table 12-4 - LEROS ITT patients with CRR from Nadir at 24 months

Patients with CRR from	with CRR from Variable		Analysis sets				
Nadir	Type ¹	LEROS ITT	mtDNA subgroups ⁴	Age at BL subgroups ⁴	Best VA at BL subgroups ⁴		
CRR	N	Х	Х	Х	х		
Months in treatment at CRR ²	С	Х	Х	Х	Х		
Time in treatment at CRR by follow-up ^{2,3}	N	Х	Х	Х	Х		
Change in logMAR compared to BL at 1st CRR ²	С	Х	х	Х	х		

Best change in logMAR compared to BL at 24 months ²	С	Х	Х	х	х
CRR Kaplan-Meier analysis	-	Х	Х	Х	X

¹ Variable Type: nominal (N), ordinal (O), continuous (C); 2 Only eyes with CRR from Nadir should be accounted; ³ Time in treatment categories defined in section 16; ⁴ Subgroups are to be analysed as defined in 9.3;

Outcome: Eyes with CRR and eyes that maintained CRR from Baseline after treatment discontinuation (Table 12-5) considering time symptoms onset in the most recent affected eye at BL.

Analysis method: This outcome will be analysed by means of descriptive statistics, accounting only eyes with a VA assessment at Visit 9. For the calculation maintenance of CRR, only eyes with CRR from Baseline at 24 months will be accounted.

Outcome: Patients with CRR and patients who maintained CRR from Baseline after treatment discontinuation (Table 12-5) considering time symptoms onset in the most recent affected eye at BL.

Analysis method: This outcome will be analysed by means of descriptive statistics, accounting only patients with a VA assessment at Visit 9. For the calculation maintenance of CRR, only patients with CRR from Baseline at 24 months will be accounted.

Table 12-5 – LEROS ITT CRR from Baseline and CRR from Baseline maintenance post-treatment discontinuation

		Analysis sets				
CRR from Baseline	Variable Type ¹	LEROS ITT	mtDNA subgroups ²	Age at BL subgroups ²	Best VA at BL subgroups ²	
Eyes with CRR	N	Х	Х	Х	Х	
Eyes with maintenance of CRR	N	Х	Х	X	Х	
Patients with CRR	N	Х	х	Х	X	
Patients with maintenance of CRR	N	Х	Х	X	X	

Variable Type: nominal (N), ordinal (O), continuous (C); 4 Subgroups are to be analysed as defined in 9.3;

V1.0 07 June 2021

Outcome: Eyes with CRR and eyes that maintained CRR from Nadir (as defined in section 16) after treatment discontinuation (Table 12-6) considering time symptoms onset in the most recent affected eye at BL.

Analysis method: This outcome will be analysed by means of descriptive statistics, accounting only eyes with a VA assessment at Visit 9. For the calculation maintenance of CRR, only eyes with CRR from Nadir at 24 months will be accounted.

Outcome: Patients with CRR and patients who maintained CRR from Nadir (as defined in section 16) after treatment discontinuation (Table 12-6) considering time symptoms onset in the most recent affected eye at BL.

Analysis method: This outcome will be analysed by means of descriptive statistics, accounting only patients with a VA assessment at Visit 9. For the calculation maintenance of CRR, only patients with CRR from Nadir at 24 months will be accounted.

Table 12-6 – LEROS ITT CRR from Nadir and CRR from Baseline maintenance post-treatment discontinuation

	Variable	Analysis sets				
ÇRR from Nadir	Type ¹	LEROS ITT	mtDNA subgroups ²	Age at BL subgroups ²	Best VA at BL subgroups ²	
Eyes with CRR	N	Х	Х	Х	х	
Eyes with maintenance of CRR	N	Х	Х	Х	х	
Patients with CRR	N	Х	Х	Х	х	
Patients with maintenance of CRR	N	Х	Х	Х	х	

¹ Variable Type: nominal (N), ordinal (O), continuous (C); ⁴ Subgroups are to be analysed as defined in 9.3;

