6.1 Outline of Study Procedures

All study procedures are outlined in the Schedule of Assessments shown below. A more detailed description of the study procedures performed at each visit is given in the following sections of the protocol.

Patients will be enrolled to receive 900 mg idebenone (2 tablets 3 times daily with meals) for 24 months. Starting with Baseline/Visit 1 sufficient study medication will be dispensed to last until the next visit. The patient will take the first dose of study medication on Day 1, the day of the Baseline Visit (or as instructed by the site investigator / study nurse).

The duration of study participation for each individual patient will be approximately 25 months and comprise 9 study visits (V1-V9). Before any study-specific procedures are undertaken, the patient (and parent/legal guardian if required) will have been thoroughly informed by the investigator of the purpose of the study, the relevant procedures and of patient rights and responsibilities. Patient information will be distributed in writing and signatures of consent obtained on the consent form. (See also Section 10.3).

Patient enrolled in the study will receive study medication at Baseline/Visit 1; the first study medication intake is on the day of the Baseline/Visit 1 (or as instructed by the site investigator / study nurse). During the 24 month treatment period, visits take place at Month 1, Month 3, Month 6, Month 9, Month 12, Month 18 and Month 24. Visit 8 (Month 24) is the endpoint of treatment. Visit 9 is a follow-up, 28-35 days after study medication discontinuation.

Physical examination and measurement of vital signs will be undertaken at Baseline/Visit 1 and then at Visit 4/Month 6, Visit 6/Month 12, Visit 7/Month 18 and Visit 8/Month 24.

Safety blood and urine and safety assessments will be done at each visit.

A urine or serum pregnancy test will be performed for WCBP at the baseline visit and further when clinically indicated.

Assessment of VA (assessed by ETDRS charts and reported in logMAR value) will be done at every visit.

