6.2.8 Visit 8 / Month 24 (± 1 week)

Assessments include:

Physical Examination

Vital Signs

Safety Blood analysis

Safety Urine analysis
Fundoscopic Exam
Visual Acuity (logMAR)
Urine or serum pregnancy test for WCBP when clinically indicated
Assessment of Adverse Events
Concomitant Medication
Patient compliance
Collection of Study Medication
Collection and Distribution of Patient Diary

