7.1 Visual acuity

Visual acuity in both eyes will be assessed at every visit by a specialist in ophthalmology. Patients will be refracted to ensure that, at every study visit, optimum vision at 4 meters is achieved. When measuring acuity in the right eye the left eye is covered and the patient is asked to read down logMAR chart 1 slowly letter by letter. When a letter is read correctly the examiner indicates this on the score sheet (identical to the chart layout). Only one reading of a given letter is allowed. When the patient has difficulty, he or she is encouraged to guess. The distance to the chart is 4 meters. If, however, less than 20 letters are read correctly from the 4 meter rows, the patient's distance to the chart will be reduced to 1 meter and the logMAR score is assessed at this distance in the same manner. Should the patient not be able to read any letters, the investigator will proceed to record whether VA is reduced to counting fingers (CF), hand motion (HM), light perception (LP), or no light perception. CF and HM are tested at a distance of about 30 cm from the eye. The left eye will then be tested in the same way using chart 2.

8 Safety Evaluations

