13.8 Other safety variables

No other safety data are to be analysed.

V1.0 07 June 2021

14 Deviations from the analyses planned in the current study protocol

There are currently no deviations from the CRS-1 CSP (version 1), CRS-2 CSP (version 1.0) and SNT-IV-005 CSP version 3.0 dated 06 March 2019 and SNT-IV-005 CSP addendum COVID-19 version1.0 dated 29 May 2020

15 Data analysis procedures

Statistical data analysis will be performed by 4Pharma Ltd according to current SAP.

Statistical analysis, tables and patient data listings will be performed with SAS® version 9.4 or higher for Windows (SAS Institute Inc., Cary, NC, USA).

16 Definitions

2nd eye onset

Most recent affected eye at Baseline.

Baseline (BL)

LEROS BL

NH BL

Best Visual Acuity

VA of the eye with best logMAR at the visit. However, if both eyes are off-chart, regardless of the VA, both eyes are considered as best eye.

Note: best eye at BL may not be the same as best eye at 6, 18 and 24 months or last assessment.

Clinical Relevant Benefit (CRB)

Defined as the composite of CRR and CRS, i.e, if the eye/patient has a CRR and/or a CRS then the eye/patient has also a CRB.

Clinical Relevant Recovery (CRR)

CRR is defined as improvement

or

- from "off-chart" (the equivalent of CF, HM, LP or NLP) VA to at least 1.6 logMAR value
 - of at least 0.2 logMAR value within "on-chart". Clinical Relevant Stabilization (CRS)

Is defined as maintenance of VA <1.0 logMAR in eyes with VA <1.0 logMAR at BL.

Clinical Relevant Worsening (CRW)

For any "on-chart" VA, CRW is defined as the disability to read at least 10 additional letters (equivalent to two chart lines) or a worsening to off-chart values (the equivalent of CF, HM, LP or NLP).

SNT-IV-005 Statistical Analysis Plan

Confidential

Delta onset

Is the time between symptoms onset of both eyes: date 2nd symptoms onset – date 1st symptoms onset. Patients will not be considered for calculating Delta onset if only one eye is affected or both eyes have the same date of symptom onset.

Months in Treatment

Months in treatment is only applied to LEROS patients. It is defined as time since BL to last follow-up during treatment period.

Nadir

Is the defined when VA reaches its worst point (highest logMAR or off-chart value). Time of nadir is the first time that nadir is reached.

Off-Chart

It is considered off-chart any VA entered as

- CF, HM, LP or NLP
- Any value above 1.68 logMAR

Patients ≤1 year after the onset of symptoms

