mean (SD ; SE)	xx.xx (xx.xx; xx.xx)	xx.xx (xx.xx ; xx.xx)	xx.xx (xx.xx ; xx.xx)
median (Q ₁ – Q ₃)	xx.xx (xx.xx – xx.xx)	xx.xx (xx.xx – xx.xx)	xx.xx (xx.xx – xx.xx)
min-max	xx.xx - xx.xx	xx.xx – xx.xx	xx.xx – xx.xx

Table 19-6 - Table shell for Safety population

Table Description	Safety Population
Categorical variable, N	xx
Category 1 n (%)	xx (xx.x%)
Category 2 n (%)	xx (xx.x%)
	xx (xx.x%)
Continuos variable, N	xx
mean (SD ; SE)	xx.xx (xx.xx ; xx.xx)
median (Q₁ – Q₃)	xx.xx (xx.xx – xx.xx)
min-max	xx.xx - xx.xx

Table 19-7 - Table shell for Survival Analysis using Kaplan-Meier method

Variable in analysis	6 months	12 months	18 months	24 months	Last Visit*
ITT patients	,		,		
At risk, n (%) ¹	xx (xx.x%)				
Event, n (%) ¹	xx (xx.x%)				
Censored, n (%) ¹	xx (xx.x%)				
KM, [95%CI] ²	xx.x% [xx.x,xx.x]				
RKM, [95%CI] ³	xx.x% [xx.x,xx.x]				
SE ⁴	xx.x	xx.x	xx.x	xx.x	xx.x
Subgroup 1					
At risk, n (%) ¹	xx (xx.x%)				
Event, n (%) ¹	xx (xx.x%)				
Censored, n (%) ¹	xx (xx.x%)				
KM, [95%CI] ²	xx.x% [xx.x,xx.x]				
RKM, [95%CI] ³	xx.x% [xx.x,xx.x]				
SE ⁴	xx.x	xx.x	xx.x	xx.x	xx.x
Subgroup					l.
At risk, n (%) ¹	xx (xx.x%)				
Event, n (%) ¹	xx (xx.x%)				
Censored, n (%) ¹	xx (xx.x%)				
KM, [95%CI] ²	xx.x% [xx.x,xx.x]				
RKM, [95%CI] ³	xx.x% [xx.x,xx.x]				
SE ⁴	XX.X	xx.x	xx.x	xx.x	xx.x

¹ n (%) values are presented as frequency and percentages; ² KM: Kaplan-Meier estimate; ³ RKM: Reverse Kaplan-Meier estimate; ⁴ SE: Standard Error

Study: SNT-IV-005

V1.0 07 June 2021

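### If the CRR Kaplan–Meier curve runs on elapsed months, the natural reading of SAP 12.3, its end overstates recovery and its 6-month reading understates it

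*SAP*

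**What the plan says.** For eyes and for patients, and for CRR from baseline and from nadir, SAP 12.3 adds a Kaplan–Meier analysis to the descriptive tables. It takes "months in treatment at CRR as time of event, and months at last assessment during treatment as censoring". SAP section 16 says of months in treatment: "It is defined as time since BL to last follow-up during treatment period". Table 12-1 lists "Months in treatment since BL at CRR" as a continuous variable. It also lists a separate nominal variable for the follow-up interval in which CRR occurred.

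On when CRR can be seen, Protocol 6.1 says "visits take place at Month 1, Month 3, Month 6, Month 9, Month 12, Month 18 and Month 24", and Protocol 7.1 says "Visual acuity in both eyes will be assessed at every visit by a specialist in ophthalmology". Each follow-up visit has a window of ±1 week (Protocol 6.2). SAP 12.4 allows COVID-19 rescheduling of up to 90 days for Visits 6 and 7, and lets Visit 8 take place up to 60 days late. SAP section 9 keeps unscheduled assessments out of summary tables.

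The output shell is "Table 19-7 - Table shell for Survival Analysis using Kaplan-Meier method". Its columns are 6, 12, 18 and 24 months and a Last Visit column whose asterisk has no explanation in the text available.

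**The concern.** CRR is interval-censored: it arises at some time between two visits and is recorded at the later one. If events and censorings are placed on the actual visit day, the spread of visit days inside a window enters the estimate, although it says nothing about recovery.

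This has two consequences. At Visit 8 every remaining eye either has its event or is censored that day, so the risk set empties through the window and late events get very large weights. At a landmark such as 6.0 months, about half of that visit's assessments fall after the mark and are not yet counted.

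The curves are planned for the ITT population and every subgroup, by eye and by patient. They bear on the objective about duration of treatment (SAP 3.2). The end of the curve is easy to quote, and its error favours the treatment.

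**Working it through.** The plan gives no expected Kaplan–Meier rate, so there is no figure of its own to reproduce.

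**Inputs from the documents.** Visits at Months 1, 3, 6, 9, 12, 18 and 24; a window of ±7 days, so 15 calendar days; 80 patients (160 eyes) and 30% drop-out (SAP section 6).

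**Assumed inputs.** The documents give no CRR rate per visit for LEROS. The expanded access programme (EAP) eye rates in Protocol 1.2 serve as a proxy: 24.2% at 6 months, 29.8% at 12 months and 39.9% at last observation, the last used for 24 months. Visit days are taken as uniform over the window, and the other visits are interpolated.

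**End of the curve.**
- At constant hazard, the share without CRR at Month 18 is √(0.702 × 0.601) = 0.650.
- The conditional probability of first CRR at Visit 8 is h = 1 − 0.601/0.650 = 0.0754.
- On nominal time the survival factor at Visit 8 is 1 − h = 0.925.
- On elapsed days, with r of the 15 days left, a share 1/r of the remaining eyes is seen that day, so the daily hazard is h/r. The factor is the product over r = 1 to 15 of (1 − h/r) = 0.775.
- The end of the curve reads 1 − 0.650 × 0.775 = 49.6%, against 39.9%: an excess of 9.7 points.
- If only 2 points of CRR arise at Visit 8, h = 0.02/0.65 = 0.031 and the end reads about 41% against 37%. Simulations gave 41% to 42%, an excess of about 4 to 5 points.

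**6-month reading.** Between 7/15 and 8/15 of the Month 6 visits fall after the mark.
- With Month 3 at 12.9%, the increment is 24.2 − 12.9 = 11.3 points, and the loss is 5.3 to 6.0 points.
- With equal steps at Months 1, 3 and 6, the increment is 24.2/3 = 8.1 points, and the loss is 3.8 to 4.3 points.

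**At-risk count at 24 months.** About 160 × 0.65 × 0.70 = 73 eyes reach Visit 8 without CRR. The count at 24.0 months holds only 7/15 to 8/15 of them, that is 34 to 39 eyes: those whose Visit 8 was on or after the mark.

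**Simulation.** Each data set (80 patients, two eyes each, ±7 whole days, 30% drop-out) was analysed once by day and once by nominal visit month. The table shows elapsed minus nominal, in points.

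| Assumed CRR | End of curve | 6 months |
|---|---|---|
| EAP eyes, Month 3 at 12.9% | +10.1 (50.2% vs 40.1%) | −5.7 |
| EAP eyes, equal steps to Month 6 | +10.3 (50.3% vs 40.0%) | −4.0 |
| EAP patients (30.6/36.2/49.3%) | +11.3 | −7.1 |
| Assumed 20/28/36% | +8.0 | −4.9 |
| Constant hazard to 40% | +15.4 | −3.0 |
| Constant hazard to 50% | +15.8 | −3.9 |
| Plateau (24/30/33%) | +3.8 | −5.7 |

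Across these rates, with 40, 80 or 160 patients and several spreads of visit dates including COVID-type delays, the end of the curve is about 4 to 25 points too high and the 6-month reading about 3 to 7 points too low. The 24-month reading is 0 to 4 points too low (39.1% against 40.0% in the second row), because uncounted late events and the shrinking risk set nearly cancel there.

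**Rounding.** With the EAP eye rates, months rounded to one decimal still give 47% to 48% at the end of the curve. Whole months give about 40% there and about 24% at 6 months, so both errors vanish when visits stay within ±1 week. A Visit 8 that is 60 days late rounds to Month 26 (24 + 60/30.4), so whole months do not protect against COVID-19 delays.

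**The case against.** The SAP nowhere says that actual visit dates are used. A continuous type is compatible with whole months, and on nominal or whole months within the window neither error arises. This stands: elapsed time is an inference. It is a good one, because a nominal-month variable would largely duplicate the follow-up category listed beside it, but it is not the SAP's text.

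A reader might infer that recovery will be inflated by 10 points. The documents do not support a fixed figure. The EAP rates are CRR from nadir, with different denominators at each time (124, 94 and 138 eyes), and the last observation came at a mean of 15.4 months (range 2.8 to 36.2). The size depends mainly on how much CRR first appears at Visit 8. A formula for untied dates, h × (ln N + 0.58) with N = 73, would give about 55%. It overstates the effect because the window has only 15 calendar days and fellow eyes share a visit.

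A reader might also infer that the efficacy conclusion is at risk. It is not. The analysis is labelled complementary, uses LEROS data only and has no test. No objective on time to recovery exists, and the comparative results at 6, 12, 18 and 24 months come from logistic regression. The CRR counts in the same tables would help to expose a discrepancy.

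Finally, reading the Last Visit column as the end of the curve is plausible but not stated.

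**Conclusion.** The point holds on the natural reading of SAP 12.3. If elapsed months are used, the end of the Kaplan–Meier curve overstates recovery, and so does the Last Visit column if it reports that end. The excess is about 10 points with the EAP eye rates, about 4 to 5 if only 2 points of CRR arise at Visit 8, and about 4 to 25 over the range of assumptions tried. The 6-month reading is about 3 to 7 points too low. The 24-month estimate is nearly right, but its at-risk row is misleading.

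The directions follow from the visit schedule and did not change in any scenario; the sizes rest on assumed CRR rates and visit-date spreads. Neither error arises on nominal months. The effect is confined to a complementary, single-arm description.

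**What to change.** In SAP 12.3, state the time scale by one of two routes:

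- Set event and censoring times to the nominal visit month (1, 3, 6, 9, 12, 18, 24), with events before censorings at ties.
- Keep the actual dates and use an interval-censored (Turnbull) estimator.

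In Table 19-7, define the Last Visit column or drop it; on nominal months it equals the 24-month column.

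The cost is a sentence in the SAP and a change of time variable or estimator in the program. The printed last-visit rate becomes less favourable. Nominal months would also date recovery early for visits delayed under the COVID-19 rules, by up to 90 days at Visits 6 and 7. The interval-censored estimator avoids that.
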